9.4.3 Evaluating Adverse Events

An Investigator who is a qualified physician will evaluate all adverse events with respect to the elements outlined in Table 4. The Investigator's assessment of causality is required for each adverse event. Refer to Table 4 for instructions in evaluating adverse events.

Approved by:
[name]

Protocol No. SARO.16.004
Version No.: 6.0

Table 4. Evaluating Adverse Events

Maximum Intensity	Mild	awareness of sign or symptom, but easily tolerated
	Moderate	discomfort enough to cause interference with usual activity (for pediatric trials, definitely acting like something is wrong)
	Severe	incapacitating with inability to work or do usual activity (for pediatric trials, extremely distressed or unable to do usual activities)
Seriousness	A serious adverse event (AE) is any adverse event occurring at any dose or during any use of Sponsor's product that:	
	† Results in death ; or	
	† Is life threatening ; or places the subject, in the view of the Investigator, at immediate risk of death from the event as it occurred [Note: This does not include an adverse event that, had it occurred in a more severe form, might have caused death.]; or	
	† Results in a persistent or significant disability/incapacity (substantial disruption of one's ability to conduct normal life functions); or	
	† Results in or prolongs an existing inpatient hospitalization (hospitalization is defined as an inpatient admission, regardless of length of stay, even if the hospitalization is a precautionary measure for continued observation. (Note: Hospitalization [including hospitalization for an elective procedure] for a pre-existing condition which has not worsened does not constitute a serious adverse event.); or	
	† Is a congenital anomaly/birth defect (in offspring of subject taking the product regardless of time to diagnosis); or	
	Is a cancer ; or	
	Is associated with an overdose (whether accidental or intentional). Any adverse event associated with an overdose is considered a serious adverse event. An overdose that is not associated with an adverse event is considered a non-serious event of clinical interest and must be reported within 24 hours.	
	Other important medical events that may not result in death, not be life threatening, or not require hospitalization may be considered a serious adverse event when, based upon appropriate medical judgment, the event may jeopardize the subject and may require medical or surgical intervention to prevent one of the outcomes listed previously (designated above by a †).	
	Duration Record the start and stop dates of the adverse event. If less than 1 day, indicate the appropriate length of time and units	
Action taken	Did the adverse event cause the Sponsor's product to be discontinued?	
Relationship to Sponsor's Product	Did the Sponsor's product cause the adverse event? The determination of the likelihood that the Sponsor's product caused the adverse event will be provided by an Investigator who is a qualified physician. The Investigator's signed/dated initials on the source document or worksheet that supports the causality noted on the AE form, ensures that a medically qualified assessment of causality was done. This initialled document must be retained for the required regulatory time frame. The criteria below are intended as reference guidelines to assist the Investigator in assessing the likelihood of a relationship between the test drug and the adverse event based upon the available information.	
	The following components are to be used to assess the relationship between the Sponsor's product and the AE ; the greater the correlation with the components and their respective elements (in number and/or intensity), the more likely the Sponsor's product caused the adverse event:	
	Exposure	Is there evidence that the subject was actually exposed to the Sponsor's product such as: reliable history, acceptable compliance assessment (pill count, diary, etc.), expected pharmacologic effect, or measurement of drug/metabolite in bodily specimen?
	Time Course	Did the AE follow in a reasonable temporal sequence from administration of the Sponsor's product? Is the time of onset of the AE compatible with a drug-induced effect (applies to trials with investigational medicinal product)?
	Likely Cause	Is the AE not reasonably explained by another aetiology such as underlying disease, other drug(s)/vaccine(s), or other host or environmental factors
Relationship to Sponsor's Product (continued)	The following components are to be used to assess the relationship between the Sponsor's product and the AE: (continued)	
	Dechallenge	Was the Sponsor's product discontinued or dose/exposure/frequency reduced? If yes, did the AE resolve or improve? If yes, this is a positive dechallenge. If no, this is a negative dechallenge. (Note: This criterion is not applicable if: (1) the AE resulted in death or permanent

**Zydus Discovery
DMCC**

CLINICAL TRIAL PROTOCOL

Saroglitazar Magnesium – Phase II

SARO.16.004

CONFIDENTIAL

PAGE 71 OF 82

		disability; (2) the AE resolved/improved despite continuation of the Sponsor's product; (3) the trial is a single-dose drug trial); or (4) Sponsor's product(s) is/are only used one time.)
	Rechallenge	
Was the subject re-exposed to the Sponsor's product in this trial? If yes, did the AE recur or worsen? If yes, this is a positive rechallenge. If no, this is a negative rechallenge. (Note: This criterion is not applicable if: (1) the initial AE resulted in death or permanent disability, or (2) the trial is a single-dose drug trial); or (3) Sponsor's product(s) is/are used only one time.)
 
NOTE: IF A RECHALLENGE IS PLANNED FOR AN ADVERSE EVENT WHICH WAS SERIOUS AND WHICH MAY HAVE BEEN CAUSED BY THE SPONSOR'S PRODUCT, OR IF RE-EXPOSURE TO THE SPONSOR'S PRODUCT POSES ADDITIONAL POTENTIAL SIGNIFICANT RISK TO THE SUBJECT THEN THE RECHALLENGE MUST BE APPROVED IN ADVANCE BY THE U.S. CLINICAL MONITOR AND THE INSTITUTIONAL REVIEW BOARD/INDEPENDENT ETHICS COMMITTEE.

	Consistency with Trial Treatment Profile	Is the clinical/pathological presentation of the AE consistent with previous knowledge regarding the Sponsor's product or drug class pharmacology or toxicology?
The assessment of relationship will be reported on the case report forms /worksheets by an Investigator who is a qualified physician according to his/her best clinical judgment, including consideration of the above elements.		
Record one of the following:		Use the following scale of criteria as guidance (not all criteria must be present to be indicative of a Sponsor's product relationship).
Yes, there is a reasonable possibility of Sponsor's product relationship.		There is evidence of exposure to the Sponsor's product. The temporal sequence of the AE onset relative to the administration of the Sponsor's product is reasonable. The AE is more likely explained by the Sponsor's product than by another cause.
No, there is not a reasonable possibility of Sponsor's product relationship		Subject did not receive the Sponsor's product OR temporal sequence of the AE onset relative to administration of the Sponsor's product is not reasonable OR there is another obvious cause of the AE. (Also entered for a subject with overdose without an associated AE.)

All AEs, serious and non-serious, will be fully documented on the appropriate eCRF(s). For each AE, the Investigator will provide the onset, duration, intensity, treatment required, outcome and action taken with the IP. The Investigator will determine the relationship of the IP to all AEs.

Fatal or life-threatening, unexpected adverse drug reactions (ADRs) occurring in *clinical investigations* qualify for expedited reporting. Regulatory agencies shall be notified (e.g., by telephone, facsimile transmission, or in writing) as soon as possible but no later than 7 calendar days after first knowledge by the sponsor that a case qualifies, followed by as complete a report as possible within 8 additional calendar days.

Serious, unexpected ADRs that are not fatal or life-threatening must be filed with the regulatory agency as soon as possible but no later than 15 calendar days after first knowledge by the sponsor that the case meets the minimum criteria for expedited reporting.

Approved by:
[name]

Protocol No. SARO.16.004
Version No.: 6.0

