5.5 BLINDING / UNBLINDING

The study is a double blind study, hence study participants and investigator will not be made aware which preparation (Saroglitzaz magnesium 2 mg or Saroglitzaz magnesium 4 mg or placebo), is to be administered. The randomization code will be available to the Investigator, for emergency purposes only. The randomization code will be available on each kit which is concealed in the form of scratchcard. In an emergency, when knowledge of the patient's treatment assignment is essential for the clinical management or welfare of the patient, the investigator should make every effort to first contact the Sponsor/ designee.

The formulation of Saroglitzaz magnesium (2 mg and 4 mg) and placebo IPs will be similar in appearance to make any difference in treatment unobvious to the patients and to maintain adequate blinding of evaluators. Neither the Investigator nor the patient should be able to identify the received treatment.

In an emergency, when knowledge of the patient's treatment assignment is essential for the clinical management or welfare of the patient, the investigator should make every effort to first contact the Sponsor/ designee.

Prior to unblinding the patient's treatment assignment, the investigator should assess the relationship of an adverse event to the administration of the study drug (Yes or No). If the

Approved by:
[name]

Protocol No. SARO.16.004
Version No.: 6.0

blind is broken for any reason, the investigator must record the date and reason for breaking the blind on the appropriate electronic Case Report Form (eCRF) and source documents.

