9.2.4 Source documents

Source documents provide evidence for the existence of the subject and substantiate the integrity of the data collected. Source documents are filed at the Investigator's site. Data reported on the eCRFs that are derived from source documents (SDs) must be consistent with the SDs or the discrepancies must be explained.

The Investigator may need to request previous medical records or transfer records, depending on the trial; also current medical records – not just shadow charts – must be available.

The following data to be reported on the eCRF should be included and derived from the source documents:

- Subject identification (subject number, gender, date of birth/age)
- Subject participation in the trial (substance, trial number, patient number, date informed consent given)
- Dates of subject's visits
- Medical history
- Medication history
- AEs (onset and end)
- SAEs (onset and end)
- Originals or copies of laboratory results: All laboratory reports must be reviewed by the Investigator and/or his/her designee; any abnormal findings should be addressed.

**Zydus Discovery
DMCC**

CLINICAL TRIAL PROTOCOL

Saroglitazar Magnesium – Phase II

SARO.16.004

CONFIDENTIAL

PAGE 66 OF 82

- Conclusion of subject's participation in the trial.

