8.3.2 Adverse Events

The applicable definition of an Adverse Event (AE) is in the study protocol. All AEs occurring from when a patient signs informed consent to when a patient exits the study will be accounted for in the reporting. Analysis and presentation of AEs occurring during the screening period will be separated from those occurring during the investigational period where a comparative evaluation of treatment-emergent AEs is intended. A treatment-emergent AE is an event not present prior to exposure to investigational product or any pre-existing event that worsens following exposure to investigational product. The period for treatment-emergent AE analysis starts from the first exposure to the investigational product until the patient exits the study.

Descriptive summaries (frequencies and percentages) for specific AEs will be presented by system organ class and preferred term according to the Medical Dictionary for Regulatory Activities (MedDRA Version 19.1) dictionary by treatment group and overall. In addition to an overall presentation of all AEs, reports will be generated for special classes of AEs such as investigational product related AEs, serious AEs, Maximum severity and AEs resulting in treatment discontinuation by treatment group. These reports will be supported by individual patient listings, as necessary.

Document Title:	Statistical Analysis Plan		
Version Number:	2.0	Date:	11 Nov 2019
Protocol Number:	SARO.16.004	Sponsor Name:	Zydus Discovery DMCC

Adverse events will be counted by the number of events as well as the number of subjects. For the summaries which count the number of patients by treatment group and overall, multiple AEs with the same MedDRA preferred term within the same patient will only be counted once.

Descriptive summaries (frequencies and percentages) for number of subjects experiencing AEs will also be presented.

Only patient listings will be provided for AEs that occur after signing informed consent but prior to exposure to investigational product. These listings will comprise all events occurring during this period in any patient who consented to participate in the study.

These listings will at least contain but not limited to information such as onset and resolution times, maximum severity, causal relationship to study treatment and action taken.

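### Table 4's Exposure row lets blinded investigators count treatment-revealing evidence when they rate whether an adverse event is drug-related

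*Protocol*

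**What the plan says.** Protocol 9.4.3, Table 4, sets out how an investigator judges whether the sponsor's product caused an adverse event. The Exposure row asks whether there is evidence that the subject was really exposed. Its examples start with "reliable history, acceptable compliance assessment (pill count, diary, etc". They end with "expected pharmacologic effect, or measurement of drug/metabolite in bodily specimen", and the items are joined by *or*.

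The table makes the elements cumulative: "the greater the correlation with the components and their respective elements (in number and/or intensity"), the more likely it is that the product was the cause. Evidence of exposure is the first of the three criteria for a *Yes* rating. For a *No* rating, one sufficient reason opens with "Subject did not receive the" sponsor's product. The status of the whole is advisory: "The criteria below are intended as reference guidelines to assist the Investigator", and not every criterion has to be met.

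On blinding, Protocol 5.5 says: "Neither the Investigator nor the patient should be able to identify the received treatment". It also has causality judged before any code break. On access to results, Protocol 9.2.4 says: "All laboratory reports must be reviewed by the Investigator and/or his/her designee". SAP 8.3.2 plans tables of "investigational product related AEs, serious AEs, Maximum severity and AEs resulting in treatment discontinuation by treatment group", in addition to an overall presentation of all events.

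**The concern.** In a placebo-controlled trial, whether a patient was exposed to the active product is the treatment assignment itself. History and tablet counts tell the investigator only that study tablets were taken. A visible drug effect or a measured drug level points to what the tablets contained. Table 4 accepts both kinds of evidence, and says that more evidence makes causation more likely.

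If an investigator uses the second kind, a patient whose ALP has fallen gains an element towards *Yes*, and a patient whose ALP has not moved does not. Two identical events could then be rated differently for a reason that follows the arm. The non-receipt reason adds to this, because it can be read as covering a patient thought to be on placebo.

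At stake is the comparability of the by-arm table of related events, with 12 patients planned per arm. Relatedness also enters the grade 3 item of the discontinuation list in Protocol 4.4.1.

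**Working it through.** The documents give no rate at which events are called related and no power calculation (SAP 4 says no formal sample size estimation was done). There is no planned figure to reproduce. The check is first textual, then a labelled illustration.

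**1. Can the assessor see a drug effect?** For ALP, on the text, yes.
- Both doses are said to have favourable effects on ALP and GGT (Protocol 5.7).
- Baseline is known to the site: ALP at least 1.67 times ULN at two visits, with less than 30% variance (4.2).
- Week 2 liver tests are run at the local laboratory (7.1).
- All laboratory reports are reviewed at the site (9.2.4).
- The event-of-clinical-interest rule in 9.4.4 uses ALP below 2 times ULN, which presupposes that on-treatment ALP is available.
- No passage masks ALP or lipids. The central laboratory manual mentioned in 6.2 was not available, so this rests on the protocol and SAP alone.

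**2. Can the assessor see drug levels?** Not shown. Pharmacokinetic samples go to a central laboratory, for 6 x 3 = 18 of 36 planned subjects (7.3). No passage returns concentrations to sites.

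**3. Does the evidence affect the rating?** It may. The items are alternatives, so history and tablet count can meet the Exposure element in every arm. Because elements are cumulative, a visible effect can add weight beyond the tablet count.

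**4. Which outputs use the rating?** The by-arm table of related events (SAP 8.3.2) and the grade 3 discontinuation item (Protocol 4.4.1). That item speaks of a probable or possible relation, whereas Table 4 records only *Yes* or *No*, so the link is by sense. The all-event tables and the ALP analysis do not use it.

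**5. Illustration.** All rates are assumptions. Let a be the proportion of subjects with an event, equal in all arms. Let q0 and q1 be the chance that it is called related on placebo and on active drug. Then:

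expected subjects with a related event per arm = 12 x a x q

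artificial difference in percentage points = 100 x a x (q1 - q0)

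With q0 = 0.30:

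| a | Placebo | Active, q1 = 0.30 | Active, q1 = 0.40 | Active, q1 = 0.60 | Difference (points) |
|---|---|---|---|---|---|
| 0.30 | 1.08 | 1.08 | 1.44 | 2.16 | 0, 3, 9 |
| 0.50 | 1.80 | 1.80 | 2.40 | 3.60 | 0, 5, 15 |
| 0.70 | 2.52 | 2.52 | 3.36 | 5.04 | 0, 7, 21 |

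Example: 12 x 0.50 x 0.40 = 2.40 against 12 x 0.50 x 0.30 = 1.80, and 100 x 0.50 x 0.10 = 5 points. If only arm-neutral evidence of exposure is used, this source of difference disappears. Then q1 = q0 and the difference is 0 in every row.

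**The case against.** The strongest reply is that this is generic guidance which a sensible investigator will apply neutrally. Much of that stands. The first two examples in the Exposure row are arm-neutral, and they match what the trial collects: tablet counts and accountability logs (5.12), a supervised first dose (5.6) and on-site dosing at scheduled visits (5.2). The criteria are advisory and defer to clinical judgement. Placebo is itself listed among the study drugs (5.1.1), so non-receipt can be read as having taken no study tablets. Safety is descriptive with no hypothesis (SAP 8.2), and all events are tabulated whatever their rating.

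Several stronger readings are tempting, and the documents do not support them:

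- *Table 4 instructs investigators to guess the arm.* It permits treatment-revealing evidence as one of several alternatives. It does not require it, and it leaves the order in 5.5 (causality first, unblinding after) unchanged.
- *Drug levels will bias the ratings.* No passage gives sites the concentrations.
- *Serious events will escape expedited reporting.* Through 7 days after treatment stops, serious events go to the sponsor within 24 hours whether or not related (9.4.2). After that, the investigator's view of relatedness does matter. Even so, a loss needs an investigator to set aside the tablet count and infer non-exposure from a flat ALP, and nothing shows that this happens.
- *Related events will be inflated on active drug by some stated ratio.* Any such ratio must assume that *Yes* is likelier when an effect is visible, which is the point in question. With equal probabilities the ratio is 1.0.

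What survives is that history and tablet counts do not cancel the cumulative rule, and that the non-receipt wording is ambiguous in a blinded trial.

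**Conclusion.** This is a cheap improvement, not a flaw in the main results. Table 4 allows a blinded causality rating to draw on evidence that depends on the arm, and one reason for *No* can be read as placebo assignment. Because on-treatment ALP and lipids are not masked from sites in these documents, relatedness ratings can differ by arm for identical events.

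The size cannot be derived. It is 0 if raters rely on history and tablet counts, and 3 to 21 percentage points in the illustrative cases where 40% to 60% of active-arm events are called related against 30% on placebo. None of those rates comes from the documents. The likely direction, towards more related events on active drug, is an inference. The effect is confined to the by-arm table of related events and the grade 3 discontinuation item.

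**What to change.** Make these changes to Table 4:

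1. In the Exposure row, delete the two treatment-revealing examples (expected drug effect and drug or metabolite measurement).
2. Define exposure by arm-neutral evidence (dispensing records, dosing history, tablet count). State that every patient who took at least one study tablet is treated as exposed to the sponsor's product for the causality rating.
3. Limit the non-receipt reason for a *No* rating to patients who took no study tablet.

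The cost is a few lines of text and a line in site training. No new data are needed. ALP and lipids stay visible to sites, but they no longer count as evidence of exposure. The downside is that somewhat more placebo-arm events may be rated related. If events have already been rated under the present wording, the report can say so and rest the between-arm comparison on all treatment-emergent events, which SAP 8.3.2 already provides for.

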9.4.4 Events of Clinical Interest

Selected non-serious and serious adverse events are also known as Events of Clinical Interest (ECI) and must be reported within 24 hrs to CRO/Sponsor Clinical Safety following the same procedures as outlined in Section 9.4.2. Sponsor Contact information can be found in the Investigator Trial File Binder (or equivalent).

An elevated AST or ALT lab value that is greater than or equal to 3X the upper limit of normal and an elevated total bilirubin lab value that is greater than or equal to 2X the upper limit of normal and, at the same time, an alkaline phosphatase lab value that is less than 2X the upper limit of normal, as determined by way of protocol-specified laboratory testing or unscheduled laboratory testing.*

*Note: These criteria are based upon available regulatory guidance documents. The purpose of the criteria is to specify a threshold of abnormal hepatic tests that may require an additional evaluation for an underlying etiology.

